12.8.3 Handling of Missing Data

The method of multiple imputation will be used (see Missing Efficacy Data Imputations section).

12.8.4 Multicenter Issues

The clinical study will be conducted under a common protocol for each investigational site with the intention of pooling the data for analysis. Every effort will be made to promote consistency in study execution at each investigational site. The study is intended to be conducted in a manner such that a minimum of 18 subjects will be enrolled for any investigator (i.e., approximately 6 subjects in each of the IDP-126 Gel and Epiduo® Forte arms and 3 subjects in each IDP-126 Vehicle Gel arm). In the event that there are too few subjects for an investigator, then this investigator's data will be combined, within geographic region to achieve the desired sample size minimum per arm. The combining of investigator's data will be accomplished by taking the investigator with the smallest enrollment and combining it with the investigator with the largest enrollment. If there is a further need to combine data, then the data of the investigator with the second smallest enrollment will be combined with the investigator's data which had the second largest enrollment, and so on. This process will continue for all investigators who did not have a minimum of 18 subjects. The process of combining investigator data that have insufficient subjects per treatment arm will result in redefining the groups of investigators for the purposes of statistical analyses. These combined groups will be referred to as "analysis centers" in the statistical analyses based on ANCOVA and stratified logistic testing.

Prior to investigating the treatment effect within the analysis centers, the magnitude of the site main effect will be investigated to determine if the main site-to-site variability is such that it could mask the analysis center effects. Thus, prior to pooling, the lesion count data at Week 12 will be analyzed with an ANCOVA with factors of treatment group, site, and the interaction term of treatment group by site and also the percent of subjects with treatment success at Week 12 will be analyzed with a logistic regression with factors of treatment group, site, and the interaction term of treatment group by site. If theses analyses are not computationally feasible due to some sites having very few subjects enrolled, the low enrolling sites will be excluded from these analyses.

The consistency of treatment response will be investigated across the analysis centers subsequent to combining the data as described above. Statistical tests will be conducted to identify if there

are extreme analysis centers that could affect the interpretation of common statistical and clinical conclusions. An analysis center by treatment interaction will be included in the primary variable analyses to test for parallel treatment effect at an alpha level of 0.10. Change from baseline in inflammatory lesions and non-inflammatory lesions will be analyzed with an ANCOVA with factors of treatment, analysis center, and treatment by analysis center interaction and the respective baseline lesion count variable as a covariate. For the purpose of testing consistency of treatment response, the dichotomized EGSS will be analyzed with a logistic regression procedure with factors of treatment, analysis center, and treatment by analysis center interaction. Further examination will follow for any variables that have a significant ANCOVA or logistic regression interaction term. In the event that the ANCOVA or logistic regression interaction (referred to henceforth as the "appropriate test") p-value is less than or equal to 0.10, a sensitivity analysis that excludes analysis centers with the extreme efficacy result will be performed to determine the robustness of the treatment effect. On the other hand, if the outcome of the appropriate test has a p-value greater than 0.10, then the conclusions from the pooled data will be considered to be free of the impact of extreme analysis centers.

The first step in conducting a sensitivity analysis is to identify the extreme analysis center or centers that contribute to the statistical significance of the appropriate test. The process involves submitting subsets of analysis centers to the appropriate test and observing the appropriate test p-value for the subset. Subsets with p-values greater than 0.10 for the appropriate test are considered homogeneous.

The search for an extreme analysis center begins by analyzing all subsets that can be created by excluding one analysis center. If one or more of the subsets result in an appropriate test p-value greater than or equal to 0.10, then the analysis center excluded from the subset with the largest p-value for the appropriate test is deemed to be the extreme analysis center.

If all appropriate test subset p-values are less than or equal to 0.10, then the process will analyze the appropriate test for all subsets that can be created by excluding two analysis centers. If one or more of these subsets generate appropriate test p-values larger than 0.10, then the analysis centers excluded from the subset with the largest appropriate test p-value are deemed the extreme analysis centers.

Thus, the process of identifying the extreme analysis centers will continue in a stepwise manner by first excluding one, then two, then three, etc., analysis centers until the appropriate test p-value exceeds 0.10.

Once the extreme analysis center or centers have been identified, then the treatment p-values of the remaining analysis centers will be computed. Inferences will be drawn from the treatment p-value, as well as any pertinent observations regarding the extreme analysis center or centers. Additionally, it is noted that this process excludes subjects from the analysis in a non-random manner and has an unpredictable impact on the power of the treatment effect test. In the event that the treatment effect of the remaining subset is not statistically significant, due consideration

of the post-hoc aspects of the process will be given when the results are interpreted. Conclusions will be presented by the sponsor as appropriate to the findings of the sensitivity analysis.

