12.1.3 Non-Inferiority for Lesion Count Variables Evaluator's Global Severity Score

This section provides the basic model and statistical approach which is used in combination with the multiple imputation procedures described in Section 12.1.9. Non-inferiority of IDP-126 Gel to Epiduo[®] Forte will be assessed with 95% confidence intervals with the following non-inferiority margins:

- Absolute change from Baseline to Week 12 in inflammatory lesion counts: 2.1
- Absolute change from Baseline to Week 12 in non-inflammatory lesion counts: 2.1
- Percentage of subjects who achieve at least a two-grade reduction from baseline and are "Clear" or "Almost Clear" at Week 12 in the Evaluator's Global Severity Score: 10%

Confidence intervals of the difference in means (IDP-126 – Epiduo[®] Forte) for the absolute change from Baseline in inflammatory and non-inflammatory lesions will be based on based on an ANCOVA with factors of treatment and analysis center and the respective Baseline lesion count as a covariate If the treatment-by-analysis center interaction effect is significant at an alpha less than 0.10, then the effect will be included in the model; otherwise it will be removed.

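### After removal of extreme centers, Section 12.8.4 rests inference on a treatment p-value, which cannot show whether the three non-inferiority results are robust

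*Combined protocol and SAP*

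**What the plan says.** Section 12.1.5 lists twelve primary comparisons. Nine are superiority tests: three each for IDP-126 against vehicle, Epiduo Forte against vehicle, and IDP-126 against Epiduo Forte. The other three are non-inferiority tests of IDP-126 against Epiduo Forte. Section 12.1.3 states that non-inferiority "will be assessed with 95% confidence intervals with the following non-inferiority margins": 2.1 inflammatory lesions, 2.1 non-inflammatory lesions and 10% for EGSS success. If the treatment-by-center interaction is significant in the lesion-count ANCOVA, "then the effect will be included in the model; otherwise it will be removed", so an interval is still produced.

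Section 12.8.4 adds a check on the primary variables. If the interaction p-value is 0.10 or less, "a sensitivity analysis that excludes analysis centers with the extreme efficacy result will be performed to determine the robustness of the treatment effect". Centers are dropped one, two, three at a time until the interaction p-value exceeds 0.10; "then the treatment p-values of the remaining analysis centers will be computed". The rule that follows is: "Inferences will be drawn from the treatment p-value", with relevant observations on the extreme centers also taken into account. The section remarks that the exclusions are not random and have an unpredictable effect on power. It asks for the post-hoc nature of the process to be weighed only in one case: "In the event that the treatment effect of the remaining subset is not statistically significant, due consideration" is to be given to it. The section names no confidence interval, margin, direction or contrast for the retained centers.

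**The concern.** The primary objective is a clinical bridge to Epiduo Forte, and the non-inferiority comparisons carry much of it. The extreme-center analysis is the plan's safeguard when centers disagree. For a non-inferiority claim, the question is whether the interval still excludes the margin once those centers are gone. A treatment p-value tests a difference of zero and never uses the margin. A sound non-inferiority result could therefore be reported as fragile because p > 0.05. A small p-value, read without its sign or contrast, could also be taken as reassurance that it does not give.

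**Working it through.** **Inputs.** 220 per active arm, and means and SDs from the table in Section 12.8.2 (Component A stands in for Epiduo Forte, as the plan does). Inflammatory reductions: 29.9 (11.9) for IDP-126, 26.7 (11.7) for Component A, 19.6 (12.1) for vehicle. Non-inflammatory: 35.5 (16.3) and 29.9 (16.4). EGSS success for Component A: 27.8%. Margins from Section 12.1.3; two-sided 0.05 from Section 12. Differences below are reductions, IDP-126 minus Epiduo Forte, so positive favours IDP-126. Covariate and center adjustment are not modelled.

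**1. Reproduce the plan's power.** Root-mean-square SDs are √((11.9² + 11.7²)/2) = 11.80 and √((16.3² + 16.4²)/2) = 16.35. SE = SD × √(2/220) = 1.125 and 1.559.
- Superiority, Φ(difference/SE − 1.96): 3.2/1.125 gives 81.2% (stated about 80%); 5.6/1.559 gives 94.9% (stated above 90%).
- Non-inferiority, Φ((difference + 2.1)/SE − 1.96): 99.7% and 99.9% (stated above 95%).

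**2. Where the two criteria part (inflammatory, 220 per arm).** Half-width = 1.96 × 1.125 = 2.21. The p-value is below 0.05 when |observed| > 2.21. Non-inferiority is met when observed > 2.21 − 2.1 = 0.11.

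| Observed | Two-sided p | 95% CI | Non-inferiority |
|---|---|---|---|
| −3.0 | 0.008 | −5.21 to −0.79 | fails |
| −1.0 | 0.37 | −3.21 to 1.21 | fails |
| +1.0 | 0.37 | −1.21 to 3.21 | met |
| +3.2 | 0.0045 | 0.99 to 5.41 | met |

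Differences of −1.0 and +1.0 give the same p-value and opposite answers on non-inferiority.

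**3. How often non-inferiority is met with p > 0.05.** For true difference D, this is Φ((D + 2.1)/SE − 1.96) − [1 − Φ(1.96 − D/SE)].
- Inflammatory, D = 0: 0.463 − 0.025 = 0.438.
- Inflammatory, D = +1: 0.787 − 0.142 = 0.645.
- Inflammatory, D = +3.2 (planning value): 0.997 − 0.812 = 0.185.
- Non-inflammatory, D = 0: 0.270 − 0.025 = 0.245. At the planning value of 5.6: 0.999 − 0.949 = 0.050.
- EGSS, both arms at 27.8%, unadjusted: SE = √(2 × 0.278 × 0.722/220) = 0.0427; Φ(0.10/0.0427 − 1.96) − 0.025 = 0.648 − 0.025 = 0.623.

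In the other direction, at D = −3 for inflammatory lesions, p < 0.05 occurs in 76.0% of trials, all against IDP-126, and non-inferiority is met in 0.3%.

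**4. Fewer retained subjects.** The documents give no retained number. With 132 per arm assumed, SE = 1.453 and the half-width is 2.85. An observed −3.0 gives p = 0.039 with non-inferiority failed; +1.0 gives p = 0.49 with non-inferiority met.

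**5. If the p-value is the three-level treatment test.** The vehicle groups are combined (Section 12), so the treatment factor can have three levels. Take means of 23.7, 26.7 and 19.6 (IDP-126 three lesions worse than Epiduo Forte) and SD 11.9. The noncentrality is n × Σ(mean − average)²/SD²; at 132 per arm it is 132 × 25.41/141.61 = 23.7. The test is significant in over 99% of trials at 132 to 220 per arm, while non-inferiority is met in under 0.5%.

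**The case against.** A reader might infer that the retained-center p-value would endorse the bridge even where IDP-126 is inferior to Epiduo Forte. The documents do not support that.
- The near-certain significance in step 5 needs the three-level test. Section 12.8.4 neither states nor excludes it. It speaks of p-values in the plural, and Section 12.1.5 lists only pairwise comparisons.
- With the pairwise contrast, a large deficit gives a small p-value that points against IDP-126. It misleads only if the sign is ignored. A small deficit usually gives p > 0.05 and no support at all.
- This is a sensitivity analysis. It cannot turn a failed Section 12.1.3 interval into a pass.
- The case where the main interval passes, the search is triggered and the retained-center interval fails is rare. In simulations of inflammatory counts with balanced centers, no true heterogeneity and at most two exclusions, it arose in 0.03–0.12% of trials at the planning difference and about 1% at equality.
- The p-value is not the only basis: observations on the extreme centers count too. The remark on non-random exclusion carries no condition; only the instruction to weigh the post-hoc aspects is tied to non-significance.
- Section 12 announces a separate SAP. The contrast may be defined there, although no such text is among the documents available.

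These points remove the stronger claim and limit the consequence. They leave the mismatch itself: for three of twelve primary comparisons, the stated quantity does not address the criterion that decided the result.

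**Conclusion.** The point holds in a limited form. For the non-inferiority comparisons, Section 12.8.4 bases inference in the retained centers on a quantity that cannot show whether the conclusion survives. On the pairwise reading, the more likely error runs against the sponsor: true non-inferiority described as not robust. For inflammatory lesions at 220 per arm, non-inferiority is met with p > 0.05 in about 44% of trials at D = 0, 65% at +1 and 19% at the planning difference. On the three-level reading the p-value carries almost no information about non-inferiority. The text leaves the choice between the readings open.

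These figures assume the retained numbers and true differences, use unadjusted normal approximations, and do not model selection by the center search. They describe how far the criteria disagree once the branch is entered. With no true heterogeneity, the 0.10 trigger is met in about 10% of trials for a given lesion endpoint (9.5–10.8% in simulation). The superiority comparisons are not affected, and the main interval still decides non-inferiority. The change should be made, but the primary decision does not depend on it.

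**What to change.** In Section 12.8.4, replace the sentence on inference with text to this effect: for the retained analysis centers, the IDP-126 minus Epiduo Forte estimate and its 95% confidence interval will be reported against the Section 12.1.3 margin for each non-inferiority comparison, and each superiority p-value will be reported with the pairwise contrast that it tests. Apply the post-hoc caution whether or not the retained-center result is significant.

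Present this as a sensitivity result beside the main interval, without a new pass/fail rule, because the retained subset is chosen from the data.

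The cost is a paragraph of wording and a few extra contrasts from models already being fitted. The downside is that a robustness statement may become less favourable. The change belongs in the plan before unblinding.

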12.8.5 Multiplicity Issues

The overall Type I error will be controlled. See Section 12.1.6 for further detail about control of Type I error across primary endpoints.

12.8.6 Windowing Rules

The timing of all study visits is relative to Baseline (Day 0). The Week 2, Week 4, and Week 8 visits should occur within \pm 3 days of the scheduled times, the Week 12 visit should occur within -3/+5 days of the scheduled time.

13 Quality Control and Quality Assurance

13.1 Study Monitoring

An Investigator Meeting and/or an initiation visit will be conducted with the principal investigator and study coordinators by the sponsor and/or its designee. During this meeting, an extensive review and discussion of the protocol, the roles of the study staff, all study procedures, source documents, and eCRFs will be conducted. Evaluation scales will be reviewed extensively, and documentation of training will be recorded for training of Sponsor-approved evaluators.

The study monitors/clinical research associates will be trained prior to study initiation. Following this training, an overview of the study disease and study material background will be understood. Specific monitoring guidelines and procedures to be followed during monitoring visits will also be presented. During the course of the study, all data will be 100% source document-verified by the monitors when possible. All subject source documents must be made available to the monitors.

The conduct of the study will be closely monitored by the sponsor following GCP guidelines. The reports of these verifications will also be archived with the study report. In addition, inspections or on-site audits may be carried out by local authorities or by the Sponsor's Quality Assurance Department. The investigators will allow the Sponsor's representatives and any regulatory agency to examine all study records, corresponding subject medical records, clinical dispensing records and storage area, and any other documents considered source documentation. The investigators agree to assist the representative, if required.

13.2 Audits and Inspections

The study will be conducted under the sponsorship of Bausch Health in conformance with all appropriate local and federal regulations, as well as ICH guidelines. Interim and end of study audits of raw data, study files, and the final report may be conducted by Bausch Health's Quality Assurance Department or designee.

The Sponsor is responsible for implementing and maintaining quality assurance and quality control systems to ensure that studies are conducted and data are generated, documented, and reported in compliance with the protocol, GCP, and applicable regulatory requirements. In addition, the sponsor will be responsible for securing agreement from all involved parties to ensure direct access to all study related study centers, source data/documents, eCRFs, and reports for the purpose of monitoring and auditing by the Sponsor, and inspection by domestic and foreign regulatory authorities.

13.3 Data Quality Assurance

All assessments performed will be accurately documented in the subject's source documents and eCRFs. The investigator or designee will enter the information required by the protocol into the source documents and eCRFs provided by the sponsor or designee. Subjects will be identified in the eCRFs by their assigned subject number only.

The investigators must read the protocol thoroughly and must follow the instructions exactly. Any deviations should be agreed to by prior discussion between the sponsor and the investigator, with appropriate written protocol amendments made prior to implementing the agreed changes. Any amendment containing major modifications (particularly if it may involve an increased risk to the subjects) will be approved by the IRB before it may be implemented. No change in the conduct of the study can be instituted without written approval from the Sponsor.

14 Ethics and Administrative Issues

14.1 Ethical Conduct of the Study

This study will be conducted in accordance with the ethical principles originating from the Declaration of Helsinki, ICH guidelines, GCP, and in compliance with local regulatory requirements. The investigator agrees, when signing the protocol, to adhere to the instructions and procedures described in it and thereby to adhere to the principles of GCP.

14.2 Ethics Review and Competent Authority Approval

This protocol, proposed informed consent/assent form, other information to subjects, and all appropriate protocol amendments will be properly reviewed and approved by an IRB or IEC and the competent authority as required. Documentation of all required approvals must be available prior to initiation of the study. The investigator must ensure that IRB or IEC and competent authority approvals are in place as required before implementation of protocol amendments or amendments to any other study documents. The name and occupation of the chairman and members of the IRB/IEC will be supplied to the Sponsor. The investigator will provide required progress reports and report all SAEs to the IRB/IEC as required by the IRB/IEC.

14.3 Written Informed Consent/Assent

Written informed consent/assent, in accordance with local clinical investigation regulations, must be obtained prior to participation in the study. Subjects less than age of consent must sign an assent for the study and a parent or a legal guardian must sign the informed consent (if subject reaches age of consent during the study they should be re-consented at the next study visit). The investigator or designee will discuss the purpose of the study with each subject, and provide a description of the study drug (including any potential and possible side effects) and the study procedures. Information must be given both in oral and written forms. Subject information will be provided in a language understandable to the subject and may not include any language that appears to waive any of the subject's legal rights or appears to release the investigator, the Sponsor, or the institution from liability or negligence.

The investigator will provide the prospective subject sufficient time to consider whether or not to participate, minimizing the possibility of coercion or undue influence and will discuss any questions the subject may have. The investigator will explain to the subject that participation in the study is voluntary and that withdrawal from the study is possible at any time without detriment to care. The consent must include acknowledgment that medical records and medical data derived from the study may be forwarded to the Sponsor or to responsible local or federal authorities.

No subject can enter the study or have any study related procedures performed before his/her written informed consent/assent has been obtained. The original signed and dated informed consent/assent form will be retained with the study records, and a copy of the signed form will be given to the subject.

An informed consent/assent template will be supplied by the sponsor or designee. Any changes to the informed consent/assent form must be agreed to by the sponsor or designee. Only consent/assent forms approved by the IRB/IEC and competent authority, as applicable, must be used.

14.4 Subject Data Protection

Subject data will be protected by ensuring that no captured data contain subject names, addresses, telephone numbers, email addresses, or other direct personally identifying information. Subject data recorded on eCRFs during the study will be documented in a coded fashion. The subject will only be identified by the subject number and year of birth. Confidentiality of subject records will be maintained to ensure adherence to applicable local privacy regulations. Other than where necessary to meet regulatory requirements, all data collected in this study will be presented in tabulated (i.e., aggregate) form and listings containing information that could be used to identify an individual subject will not be included in any public disclosures of the study data or the study results.

